8.2 ACCOUNTABILITY

The primary study accountability summary will be based on the All-implanted population:

- The summary will first account visit by visit for the contributing status of all enrolled subjects in the study, as of the time of a particular analysis. This accountability will follow the format of Table A.1 of ISO 11979-7:2018. Accountability will be summarized by treatment arm and overall.
- All discontinued subjects will have their refraction, BCDVA, and UCDVA history provided in a listing. A separate data listing for discontinuation due to adverse events will be generated as specified in Section 7.5.3.

8.3 DEMOGRAPHICS AND BASELINE PARAMETERS

8.3.1 Demographics and Baseline Measurements

Baseline values are those values collected preoperatively. If additional measures are taken later, but prior to surgery, then those later values will replace the prior measures.

Summary statistics based on the All-implanted population will be presented for the following demographic characteristics by treatment group: age and age categories (overall and by gender), gender, race, and ethnicity. The following baseline parameters will be summarized by treatment groups: preoperative refractive error, preoperative corneal astigmatism, preoperative vision level(s), preoperative cataract grade and biometry measurements including axial length.

Comparisons between the groups will be conducted to assess comparability.

Age will be calculated as of date of enrollment.

8.3.2 Operative Parameters

Data collected on the day of surgery for the study eye Operative Visit, will be summarized based on the All-implanted population for all the parameters listed on the operative visit CRF including but not limited to the following parameters: primary incision type, estimated incision size and axis, capsulotomy shape, lens extraction method, position of the IOL, type of IOL implanted, the power and the serial number of the implanted IOL and percent of all eyes successfully implanted. Furthermore, intraoperative complications in each complication class listed on the Operative Visit CRF will be summarized.

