### 5.3 REASONS NOT TO IMPLANT A STUDY IOL

At the time of cataract surgery, but prior to IOL implantation there are intraoperative adverse events that may prevent implantation of the designated IOLs for this clinical study. These criteria include, but are not limited to:

- 1) Intraoperative complications during phacoemulsification that require any other additional procedures or further intervention, e.g., vitrectomy.
- 2) Significant detachment of Descemet's membrane
- 3) Significant corneal endothelial damage
- 4) Wound burn
- 5) Capsular tear, iris incarceration or damage, posterior capsular rupture, vitreous loss or prolapse, or zonular weakness, dehiscence or rupture
- 6) Significant anterior chamber bleeding
- 7) Excessive iris mobility or need for iris manipulation
- 8) Mechanical or surgical manipulation required to enlarge the pupil prior to or at IOL implantation
- 9) Other ocular conditions or complications that could compromise IOL stability
- 10) Bag sulcus, sulcus-sulcus or unknown placement of haptics
- 11) Any method of anterior capsulotomy other than circular continuous curvilinear capsulorhexis (e.g., anterior capsular tears or any areas of 'can-opener' capsulotomy or FLACS)
- 12) Capsular fibrosis or other opacity
- 13) Optic and/or haptic damage/amputation
- 14) Inability to fixate IOL in desired position

If an operative adverse event prevents implantation of the investigational IOL and the IOL did not touch the eye, the subject should be implanted with an approved non-study IOL instead and followed until resolution or stability of that adverse event before discontinuation from the study. Later, the subject should be followed under the Investigator's normal standard of care.

If an operative adverse event prevents implantation of the investigational IOL and the IOL touched the eye, the subject should be implanted with an approved non-study IOL (if applicable). The Investigator should follow the subject through resolution of any adverse events (AEs) and then discontinue the

subject, followed under the Investigator's normal standard of care. In this case, the subject will be included in the Safety population.

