7 ANALYSIS POPULATIONS AND VISIT WINDOW

7.1 ANALYSIS POPULATIONS

The All-enrolled population includes all subjects who sign an informed consent form. This population will be used for disposition summaries.

The Safety population will include all subjects where the test or control IOL touched the eye.

The intent to treat (ITT) population includes all randomized subjects. Missing data will be imputed. Subjects will be analyzed as randomized. The ITT population is the primary analysis population for assessing effectiveness.

The All-implanted population includes all ITT subjects who were successfully implanted with one of the two study IOLs and who attended at least one postoperative visit. Missing data will be imputed. Subjects will be analyzed as randomized. The All-implanted population is supportive of the ITT population for assessing effectiveness.

The Per-Protocol (PP) population includes all subjects in the All-implanted population who have no major protocol deviations that could affect the interpretation of effectiveness and have attended the Form 4 visit. Exclusions from PP will be determined prior to study unmasking. Missing data will not be imputed. Subjects will be analyzed as treated. Analyses based on PP will be supportive of those based on All-implanted.

The Best Case Set will include subjects in PP with all of the following characteristics:

- No major protocol deviations potentially affecting any of the primary effectiveness endpoints (BCDVA, DCNVA). Major protocol deviations that may potentially affect the primary effectiveness endpoints include, but are not limited to:
 - Inclusion of ineligible subjects
 - Implantation of incorrect IOL
 - Missed assessments for effectiveness endpoints at Form 4
 - Receipt of medication likely to interfere with visual performance at Form 4
- One eye implanted with a study lens
- No clinically significant preoperative ocular pathology in the study eye, including any of the following present prior to the operative visit
 - Pseudoexfoliation
 - Glaucoma
 - Uveitis
 - Retinal detachment
 - Diabetic retinopathy
 - Macular degeneration
 - Amblyopia
 - Other preoperative pathologies that are likely to affect central acuity
- No macular degeneration detected at any time in the study eye
- No previous surgery for the correction of refractive errors in the study eye

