8.5 SAFETY ANALYSES

All co-primary safety endpoints need to be achieved to claim overall safety success. Therefore no multiplicity adjustment is necessary for primary safety endpoints. For all key safety endpoints, the primary analysis population will be the safety analysis population.

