A subject will be said to have experienced a persistent adverse event if a given adverse event is present at the conclusion of the clinical study (i.e., at database lock). The cumulative occurrence of an adverse event at an analytical time point refers to the total number of times a subject has experienced the occurrence of a given adverse effect between implantation and the conclusion of the clinical trial.

Incidence of adverse events (persistent or cumulative, as appropriate) listed in ISO 11979-7:2018 Table E.2 (Posterior chamber IOL adverse event rates will be compared to the historical control safety and performance endpoints (SPE) rates, as specified in **Section 7.5.1**. If none of the ISO-defined posterior chamber AE incidence rate is greater than the respective SPE rate, then investigational device will have met the co-primary safety endpoint on adverse event.

The AE tables will be listed by treatment group and will include the AE term, the event count, the incidence rate, and corresponding confidence intervals. The tables will be generated for the AEs listed in ISO 11979-7:2018, SAEs (separately for ocular and non-ocular), and all other AEs (separately for ocular and non-ocular). The table for the AEs listed in ISO 11979-7:2018 will also list *p*-values. The ocular AE tables may also be separately reported for device-related, procedure-related vs. non-related. If any UADE is reported in the study, they will be reported in a separate table.

Supplemental AE data listings will be ordered by subject and will list such information as AE term, treatment group, whether it is ocular or systemic, SAE (if applicable), date of onset, date of resolution, severity, relationship to the study device and relationship to the procedure. The onset of ocular adverse events will also be shown relative (in number of days) to the surgery date for that eye.

Per-subject data listings for death, SAEs, and premature discontinuation due to adverse events will also be produced.

Intraoperative adverse events are excluded from the above tables. An intraoperative AE is defined to be any adverse event with onset during surgery. Intraoperative adverse events will be presented in a data listing and summarized by treatment group.

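### SAP 8.3.2 takes the implant success rate on the All-implanted population, so it is 100% by construction, and intraoperative failures before lens contact have no assured denominator

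*SAP*

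**What the plan says.** **Operative data.** SAP 8.3.2 states that data from the day of surgery "will be summarized based on the All-implanted population for all the parameters listed on the operative visit CRF". The parameters it names end with "the power and the serial number of the implanted IOL and percent of all eyes successfully implanted". The next sentence adds: "Furthermore, intraoperative complications in each complication class listed on the Operative Visit CRF will be summarized". It names no other population.

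**Population.** Under SAP 7.1, All-implanted "includes all ITT subjects who were successfully implanted with one of the two study IOLs and who attended at least one postoperative visit". ITT is all randomized subjects. The Safety population needs only that a study lens touched the eye.

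**Failed implantation.** Protocol 5.3 recognizes that, before the lens goes in, "there are intraoperative adverse events that may prevent implantation of the designated IOLs for this clinical study". It gives 14 reasons and separates subjects by whether the lens touched the eye; only those with contact are placed in the Safety population. Protocol 7.1 does not replace randomized subjects who receive no study lens.

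**Other reporting routes.** SAP 8.5.3 takes intraoperative events out of the main adverse event tables and then says: "Intraoperative adverse events will be presented in a data listing and summarized by treatment group". Appendix B puts safety tables on the Safety population and administrative tables on Safety, ITT, All-implanted and PP. The list of tables itself is redacted.

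**Accountability.** SAP 8.2 opens: "The primary study accountability summary will be based on the All-implanted population". Its first bullet then accounts for all enrolled subjects, and SAP 7.1 assigns disposition summaries to All-enrolled.

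**The concern.** A success rate has to be computed on eyes in which success was attempted. Here the denominator is chosen by the outcome, so the figure carries no information about failed implantation in either arm.

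The complication summary has a related weakness. An event serious enough to stop implantation removes the eye from the population on which SAP 8.3.2, read in context, counts complications.

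A difference between arms would be of interest. The two lenses differ in haptic design and total diameter (11.40 mm against 13.0 mm, Protocol 6.1.1 and 6.1.2), and Protocol 8.2 gives separate instructions for their delivery systems. Some of the reasons in Protocol 5.3 concern the lens itself, such as damage to the optic or haptics and failure to fixate it where wanted.

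**Working it through.** The documents give no expected implant success rate and no count of failures, so there is no figure of the plan's own to reproduce. The check is of numerators and denominators.

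**Step 1. Where each kind of randomized eye falls, under SAP 7.1 and Protocol 5.3**

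| Randomized eye | ITT | Safety | All-implanted |
|---|---|---|---|
| Implanted, seen postoperatively | yes | yes | yes |
| Implanted, never seen postoperatively | yes | yes | no |
| Lens touched the eye, not implanted | yes | yes | no |
| Surgery begun, failed before lens contact | yes | no | no |
| No surgery | yes | no | no |

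**Step 2. The success rate.** Let n be the eyes in the intended denominator, k those not implanted, and m those implanted but never seen afterwards.

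- As written, on All-implanted: (n − k − m)/(n − k − m) = 100% for every k and m.
- On the wider denominator: (n − k)/n.

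**Step 3. Size.** SAP 6.2 plans 115 eyes per arm, 230 in all. I use these for n; k is assumed. Intervals are exact (Clopper-Pearson) 95%.

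| Assumed k | One arm, (115 − k)/115 | 95% CI | As written |
|---|---|---|---|
| 1 | 114/115 = 99.1% | 95.3% to 100.0% | 100% |
| 3 | 112/115 = 97.4% | 92.6% to 99.5% | 100% |
| 5 | 110/115 = 95.7% | 90.2% to 98.6% | 100% |
| 10 | 105/115 = 91.3% | 84.6% to 95.8% | 100% |

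Over both arms, k = 1, 3, 5 and 10 of 230 give 99.6%, 98.7%, 97.8% and 95.7%.

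**Step 4. The complication summary.** If c eyes have a complication and f of these are outside All-implanted, the literal rule gives (c − f)/(n − k − m) in place of c/n. The documents supply neither c nor f, so I put no number on this difference.

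**Step 5. What the other routes recover.** The third row of the first table is in Safety, and so is covered by summaries on that population. The fourth row is not. The intraoperative summary in SAP 8.5.3 would cover it only if its unstated denominator is wider than Safety. If that summary is one of the safety tables, Appendix B puts it on Safety and the fourth row drops out.

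**The case against.** A reader might infer from SAP 8.3.2 that every complication that prevented implantation vanishes from the report and that any difference between arms is hidden. The documents do not support that. SAP 8.5.3 promises both a listing and a by-arm summary of intraoperative adverse events and does not tie them to All-implanted. Protocol 5.3 keeps failures after lens contact in the Safety population, and SAP 8.5 states: "For all key safety endpoints, the primary analysis population will be the safety analysis population". Appendix B adds line listings behind all summary tables.

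Three further points can be made for the plan.

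- **Appendix B may already give an ITT version.** It would if operative parameters are among the administrative tables. The redaction prevents confirmation either way. If they are, Appendix B and SAP 8.3.2 name different populations and need aligning.
- **The wording may intend more.** Reference to all eyes suggests a wider denominator, and the complication sentence names no population. Both are fair, but the only population stated in the paragraph is All-implanted.
- **SAP 8.2 partly corrects itself.** Its bullet covers all enrolled subjects, and SAP 7.1 gives disposition to All-enrolled. What remains is a conflict between lead-in and bullet. A reader might go further and infer that missing data in the ITT analysis are understated. That does not follow, because the primary effectiveness analysis includes every randomized subject, with imputation.

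These points limit the concern to the 8.3.2 outputs, the pre-contact failures and the conflict in 8.2. They do not rescue the success rate as written.

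**Conclusion.** The point stands in limited form. The 100% success rate follows from the definitions alone and needs no assumption. The omission of non-implanted eyes from the 8.3.2 complication summary rests on reading that sentence with the population named just before it. The remaining gap concerns failures before the lens touched the eye: they are outside both Safety and All-implanted, and no section assures them a denominator.

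The distortion in the success rate equals the proportion of eyes not implanted, for example 0.9, 2.6 or 4.3 percentage points for 1, 3 or 5 of 115. Those counts are assumptions. Implant success is not a co-primary or additional safety endpoint, so no hypothesis test, alpha, power figure or success criterion is affected.

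**What to change.** - **SAP 8.3.2:** report implant success and intraoperative complications by randomized arm on all randomized eyes taken to surgery. Report implant success on ITT as well. The two differ because randomization takes place at the preoperative visit, so ITT also includes subjects who never reach surgery. Keep All-implanted only for descriptors of the implanted lens, such as power, serial number and position.
- **SAP 8.5.3 and Appendix B:** state the same denominator for the intraoperative adverse event summary, so that failures before lens contact are counted, and make the populations in Appendix B agree with 8.3.2.
- **SAP 8.2:** replace All-implanted in the lead-in with All-enrolled/ITT, in agreement with its own bullet and with SAP 7.1.

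The cost is SAP wording and a changed denominator in a few tables. The operative data are already collected at Form 0; no new data or change to sample size is needed.

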8.4 EFFECTIVENESS ANALYSES

All co-primary effectiveness endpoints need to be achieved to claim overall effectiveness success. Therefore no multiplicity adjustment is necessary for primary effectiveness endpoints. For the primary effectiveness endpoints, the primary analysis population will be the ITT analysis population. The All-implanted, PP, and best case analysis populations will also be used for co-primary effectiveness endpoint analysis to support the primary ITT analyses.

8.4.1 Co-Primary Effectiveness Endpoints

Co-Primary Effectiveness Endpoints

[REDACTED]

With performance goals of:

1. Statistically significant smaller residual manifest cylinder, of 0.4D or greater, in test arm than in control arm.
 2. 90% of eyes at target.
 3. 95% of eyes at target.
 4. 90% of eyes at target.
- [REDACTED]
- [REDACTED]
- [REDACTED]
- [REDACTED]

8.4.2 Secondary Effectiveness Endpoint

There are no secondary effectiveness endpoints.

8.4.3 Imputation Methods and Sensitivity Analyses for Co-Primary Effectiveness Endpoints

For ITT and All-implanted analyses, per ANSI Z80.30-2018, eyes that have a secondary surgery that is targeted to correct for postoperative toric IOL rotation shall have their clinical results prior to that surgical intervention carried forward as the final results for analysis. Further, in cases where axis misalignment measured at follow up visits after a secondary surgical intervention (SSI) is greater than the axis misalignment prior to SSI, the greater misalignment error shall be considered as the final result for analysis. Repositioning of test IOLs will result in imputation of worst observed value or assignment failure for the co-primary endpoints at Form 4 analysis, as appropriate. Imputation methods described below will retain these worst-value or failure assignments and will not overwrite them with imputed values.

For the ITT and All-implanted analysis populations missing co-primary endpoint data will be imputed where there are no available data at Form 4. The primary imputation method will be by

multiple imputation and be implemented using the MI and MI ANALYSE procedure in SAS® (Version 9.4 or later) or using the mice package (Version 3.16.0 or later) from R. A pre-specified seed of 20231026 (the date of version 1.0 of the protocol) will be used. Predictors will include attempted toric correction, age, and sex; 50 imputed datasets will be generated; the Markov Chain Monte Carlo (MCMC) method will be applied when using SAS. [REDACTED]

[REDACTED]

[REDACTED]

[REDACTED]

For all other co-primary endpoints, the [REDACTED] will be performed in which missing data are initially assumed to be failures. Then, one of the imputed failures will be imputed as a success. Then, a second failure will be assigned to a success. This process will be repeated until all missing data are imputed as successes. The point at which, if any, where the results of the hypothesis test changes its results regarding rejection of the null hypothesis will be reported.

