## 9.7 MISSING DATA AND IMPUTATION

Missing Form 4 effectiveness endpoint data will be imputed for All-implanted and ITT analyses.

For ITT, All-implanted, and PP analyses, per ANSI Z80.30-2018, eyes that have a secondary surgery that is targeted to correct for postoperative toric IOL rotation shall have their clinical results prior to that surgical intervention carried forward as the final results for analysis. Further, in cases where axis misalignment measured at follow up visits after an SSI is greater than the axis misalignment prior to SSI,

the greater misalignment error shall be considered as the final result for analysis. Repositioning of toric IOLs will result in imputation of worst observed value or assignment failure for the co-primary endpoints at Form 4 analysis, as appropriate. Imputation methods described below will retain these worst-value or failure assignments and will not overwrite them with imputed values.

The primary imputation method for all co-primary endpoints will be by multiple imputation where details of initial seed, predictors and methods will be fully described in the Statistical Analysis Plan. Co-primary endpoint 1, will use 50 imputed datasets for analysis; all other endpoints, being binary and tested by exact methods, are not amenable to combining multiple imputations, so only the first imputed dataset will be used.

In addition, for co-primary endpoint 1, where two arms are involved, a tipping point sensitivity analysis will involve initially setting all control-lens eyes with missing data to the best observed outcome (presumably, 0.0 residual cylinder) and setting all toric-lens eyes with missing data to the worst observed outcome. The best and worst values will be incremented/decremented by 0.125 D until control eyes have the worst and toric have the best value imputed. The point at which, if any, where the results of the hypothesis test changes its results regarding rejection of the null hypothesis will be reported.

For all other co-primary endpoints, the tipping-point sensitivity analysis will be performed in which missing data are initially assumed to be failures. Then, one of the imputed failures will be imputed as a success. Then, a second failure will be assigned to a success. This process will be repeated until all missing data are imputed as successes. The point at which, if any, where the results of the hypothesis test changes its results regarding rejection of the null hypothesis will be reported.

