2 INTRODUCTION

The purpose of this statistical analysis plan (SAP) is to describe the planned analyses and reporting for protocol PHY2302, version 1.1 dated 20 Feb 2024.

This SAP is being written with due consideration of the recommendations outlined in the most recent International Conference on Harmonisation (ICH) E9 Guideline entitled Guidance for Industry: Statistical Principles for Clinical Trials and the most recent ICH E3 Guideline, entitled Guidance for Industry: Structure and Content of Clinical Study Reports.

This SAP describes the data that will be analyzed and the subject characteristics, effectiveness, and safety assessments that will be evaluated. This SAP provides details of the specific statistical methods that will be used. The statistical analysis methods presented in this document will supersede the statistical analysis methods described in the clinical protocol. If additional analyses are required to supplement the planned analyses described in this SAP, they may be completed and will be identified in the clinical study report

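### SAP 8.4.3 leaves the per-protocol population out of the rotation-surgery scoring rule that protocol 9.7 applies to it, so PP and Best Case may score repositioned toric eyes differently from ITT

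*SAP*

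**What the plan says.** Protocol 9.7 sets the rule for eyes that have a second operation to correct rotation of the toric lens. Results from before that operation become the final results. If misalignment afterwards is larger than before, the larger value counts. Repositioned toric eyes take the worst observed value or are assigned failure on the co-primary endpoints, as appropriate. The scope is "For ITT, All-implanted, and PP analyses, per ANSI Z80.30-2018".

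SAP 8.4.3 repeats the paragraph nearly word for word, but its scope is "For ITT and All-implanted analyses, per ANSI Z80.30-2018". PP is not named, and the visible text gives no reason.

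Three other SAP statements matter:
- Section 2 says that the SAP's methods "will supersede the statistical analysis methods described in the clinical protocol".
- Section 8.4 plans the affected runs: "The All-implanted, PP, and best case analysis populations will also be used for co-primary effectiveness endpoint analysis to support the primary ITT analyses".
- Section 7.1 draws Best Case from PP: "The Best Case Set will include subjects in PP with all of the following characteristics". It also says that missing PP data are not imputed.

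**The concern.** The rule decides how an eye with observed data is scored. It does not fill gaps. A repositioned eye normally has a Form 4 measurement; the question is whether that measurement, taken after corrective surgery, may count. The rule prevents a lens that rotated and was surgically re-aligned from being credited with the re-aligned result.

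Only the toric arm has an axis to correct, so any credit of this kind goes to the test lens. If PP and Best Case score such eyes on corrected data while ITT scores them on pre-surgery or worst values, the supportive runs no longer check the same quantity as the run they support. Part of any agreement or disagreement could then come from the scoring rule.

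The decision on effectiveness is not at stake, because ITT is the primary population and keeps the rule.

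**Working it through.** **1. The two scope statements**

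| Item | Protocol | SAP |
|---|---|---|
| ITT under the rule | yes (9.7) | yes (8.4.3) |
| All-implanted under the rule | yes (9.7) | yes (8.4.3) |
| PP under the rule | yes (9.7) | not named (8.4.3) |
| Best Case under the rule | not named | not named |
| Missing PP data imputed | no (9.2, 9.7) | no (7.1) |

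The protocol holds both that PP data are not imputed and that the rule covers PP. It therefore treats the two as compatible, and the no-imputation policy does not explain the omission.

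**2. Can a repositioned eye be in PP?** Yes. Protocol 8.6.2 provides for repositioning, preferably within 30 days of surgery. It is not among the listed major deviations or Best Case exclusions (protocol 9.2, SAP 7.1). Form 4 falls at 120 to 180 days (SAP 7.2) and is the analysis time point (SAP 8.1). Without the rule, the default value is therefore post-surgery.

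**3. Reproducing the plan's figures, to size the effect**
- Completers: 230 × (1 − 0.13) = 200.1, so about 100 toric eyes at 1:1 (SAP 6.2).
- Co-primary 4 (protocol 9.5: assumed rate 91.46%, target 90%) passes when the upper 95% Clopper-Pearson bound reaches the target. Taking the bound as one-sided with n = 100, this needs at least 85 successes. P(X ≥ 85), X ~ Bin(100, 0.9146), is 0.9893. The plan states 99%.
- Co-primary 3 (assumed 99.0%, target 95%) needs at least 91 of 100. The power exceeds 99.9%; the plan states 99%.
- Joint power: 0.94 × 0.99 × 0.99 × 0.99 = 0.912. The plan states 91%. The 0.94 and the co-primary 2 power cannot be rebuilt because their inputs are redacted.

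**4. Effect on the binary PP rates.** Let k of 100 toric PP eyes be repositioned. The documents give no k; 0 to 5 is an assumption. The largest possible shift is k/100, or k percentage points, reached only if every such eye fails under the rule and succeeds without it.

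Under that extreme, with the other eyes at 91.46%, the chance that PP passes co-primary 4 is:
- rule applied: P(Bin(100 − k, 0.9146) ≥ 85)
- rule absent: P(Bin(100 − k, 0.9146) ≥ 85 − k)

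| k | Rule applied | Rule absent |
|---|---|---|
| 0 | 0.9893 | 0.9893 |
| 1 | 0.9791 | 0.9903 |
| 2 | 0.9610 | 0.9912 |
| 3 | 0.9306 | 0.9920 |
| 4 | 0.8830 | 0.9928 |
| 5 | 0.8133 | 0.9935 |

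For co-primary 3 the chance stays above 99.7% either way up to k = 5.

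**5. Co-primary 1.** Residual cylinder is not pass/fail per eye. If k eyes each differ by g D between the two scorings, the toric mean moves by k × g/100. For k = 1 to 5 and g = 0.25 to 1.0 D (assumed), that is 0.0025 to 0.05 D, against a performance goal of 0.4 D. The test itself is Wilcoxon, so this sizes only the reported mean difference.

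**The case against.** A reader might infer that the SAP tells the analyst to score re-aligned PP eyes on their corrected outcome. No sentence says so, and three things leave room for another handling:
- Protocol 8.6 states the carry-forward and larger-misalignment rule with no population limit. It sits among study procedures, so it is arguable that an override of statistical methods leaves it in force.
- The SAP 8.4.3 sentence assigning worst value or failure to repositioned test lenses names no population. It does stand in a paragraph whose opening words limit it to ITT and All-implanted, so the narrower reading is the natural one.
- Parts of SAP 8.4.1 and 8.4.3 are redacted, and a PP rule could be there.

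These points stand. They make the consequence a default reading, but they do not remove the conflict between two visible scope statements.

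A reader might also infer that Best Case was removed from the protocol's rule. It was never named there; it is affected only because it is drawn from PP.

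Nor does each repositioned eye turn from failure into success. Co-primary 3 asks for misalignment under 20°, so an eye repositioned at 15° already succeeds under carry-forward alone and fails only through the separate repositioning sentence. Co-primary 4 concerns change from Form 3 to Form 4, and a re-aligned eye can still miss it. The plan's own 99.0% for co-primary 3 implies about 1 failure per 100 eyes, so five conversions there would exceed its expectation. The count may also be zero, in which case nothing changes.

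Finally, PP already differs from ITT through its exclusions and lack of imputation, so a gap between them would not be purely a product of this rule.

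**Conclusion.** The inconsistency is real and confined to supportive analyses. The governing document omits PP from a scoring rule that the protocol applies to PP. On the natural reading of the visible text, repositioned toric eyes in PP and Best Case are scored on post-surgery Form 4 data, which tends to favour the toric lens.

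The binary PP rates shift by at most k percentage points for k repositioned eyes of about 100, with k assumed to be 0 to 5. In the extreme case the chance that PP passes co-primary 4 differs by about 1 point at k = 1 (0.9903 against 0.9791) and 18 points at k = 5 (0.9935 against 0.8133). Those figures rest on the assumed k, a one-sided bound, the other eyes succeeding at 91.46%, and every repositioned eye changing status. Co-primary 1 shifts only through those eyes' cylinder values.

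The documents do not support reading this as a threat to the primary effectiveness conclusion: ITT and All-implanted keep the rule and their results are unaffected.

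**What to change.** In SAP 8.4.3, replace the opening scope with the protocol's: "For ITT, All-implanted, and PP analyses, per ANSI Z80.30-2018". As an addition beyond the protocol wording, state that Best Case, as a subset of PP, follows the same rule. Make clear that the repositioning sentence has the same scope, and that the rule scores observed eyes and so is consistent with not imputing missing PP data.

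If leaving PP out was deliberate, the SAP should instead say so, justify the departure from protocol 9.7 and reconcile it with protocol 8.6. Either change should be made before unmasking.

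The cost is one phrase and one or two sentences, with no new data and no effect on sample size. PP and Best Case rates may be slightly less favourable to the toric lens.
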